6.5 CONCOMITANT THERAPY

For this protocol, participants may use antidepressants and anxiolytics at the discretion of their treating providers. Medication usage will be assessed at each study visit and documented in the eCRF.

6.5.1 RESCUE THERAPY

N/A

7 STUDY INTERVENTION DISCONTINUATION AND PARTICIPANT DISCONTINUATION/WITHDRAWAL

7.1 DISCONTINUATION OF STUDY INTERVENTION/EXPERIMENTAL MANIPULATION

At subject, PI, or study team member request.

When a subject discontinues from BRIGHT or AC but not from the study, remaining study procedures will be completed as indicated by the study protocol. The data to be collected at the time of study intervention discontinuation will include the following:

- The reason(s) for discontinuing the participant from the intervention, and methods for determining the need to discontinue
- If the participant is due to complete assessments within 2 weeks of being discontinued from the study intervention, those assessments will be administered at the time of discontinuation; if the next scheduled assessments are more than 2 weeks from the discontinuation date, the discontinued participant will wait for the next scheduled assessment. Thereafter, the participant will be included in all future scheduled assessments, even though not participating in the intervention.

7.2 PARTICIPANT DISCONTINUATION/WITHDRAWAL FROM THE STUDY

Participants are free to withdraw from participation in the study at any time upon request. The investigators will seek to minimize participant discontinuation/withdrawal from the study (see **Section 7.3, Lost to Follow-Up**) except for safety reasons.

An investigator or the IRB may discontinue a participant from the study for the following reasons:

- Significant study intervention non-compliance
- Lost-to-follow up; unable to contact subject (see **Section 7.3, Lost to Follow-Up**)
- Any event or medical condition or situation occurs such that continued collection of follow-up study data would not be in the best interest of the participant or might require an additional treatment that would confound the interpretation of the study

The date and reason for participant discontinuation or withdrawal from the study will be recorded in the eCRF.

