Responding to Physical/Emotional Distress. Measures to protect against study-related psychological and emotional distress (without suicidal/homicidal ideation) during the study intervention or follow up assessments are described below. Participants will be reminded that the decision to initiate and/or continue participating in this research is voluntary. Participants will be informed from the outset that they are free to terminate the assessments, procedures, or therapy sessions at any time and/or refrain from answering any questions that make them uncomfortable. The interviewers are trained researchers who are experienced in the conduct of interviews related to psychosocial aspects of cancer. Our past experience using these study measures suggest that data collection using these instruments can be conducted without undue psychological distress or exacerbation of symptoms among this population (HNC survivors with BID). The study participant will be encouraged to take time when answering questions and may refuse to answer any question at any time during the study.

Participants in either study condition who do NOT have current suicidal or homicidal ideation but nevertheless appear to be experiencing a high level of distress during the study will be asked if they would like to talk to one of site-Pis or associated licensed clinical psychologists. In these instances, the site PI or one of the study psychologists will contact the participant within 24 hours to assess the nature and urgency of the distress, determine the need for clinical intervention beyond any treatment that they may already be receiving, and arrange appropriate mental health referral. In the event that one of the clinical psychologists participating in the trial is not available, a licensed psychologist who works at the relevant site (MUSC, Washington University School of Medicine [WUSM], or Henry Ford Health [HFH]) will be contacted instead. Immediate backup and support will be available. As part of our initial training of the program coordinator at each site, we will work closely with the HFH and WUSM teams to identify local mental health and crisis intervention resources that can be used by Drs. [name] or [name] for referrals should a patient express significant distress in the context of the post-baseline assessment. In rare cases where a mental health referral is needed, the investigator will re-contact the participant.

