9.2 SAMPLE SIZE DETERMINATION

The primary endpoint for the proposed RCT is the change in the IMAGE-HN score from baseline to 6-month follow-up. Our primary objective is to test the hypothesis that BRIGHT decreases HNC-related BID from baseline to 6-month follow-up (as measured by clinically significant reduction in the IMAGE-HN score) relative to AC. We target a mean difference in IMAGE-HN score reduction of 9 between BRIGHT and AC at 6 months. This targeted difference is (1) clinically important using widely accepted distribution-based methods of patient reported outcome measure interpretation⁸⁸ and (2) commensurate with clinically meaningful differences in BID among cancer survivors from other appropriately powered trials.^{14,41,100} In our pilot RCT, at 3-months post-intervention (a timepoint similar to 6 month follow-up), BRIGHT improved IMAGE-HN scores from baseline relative to AC (mean model-based difference in change in IMAGE-HN score = -17.1 [90% CI, -25.6 to -8.6] points; $P = 0.002$). The targeted clinically important difference in IMAGE-HN score reduction of 9 thus appears highly feasible. Determining the sample size for the proposed RCT requires adjusting for the clustering of trial participants within psychologist (BRIGHT arm) or HN clinical staff member (AC arm). We expect the number of clusters in each arm to be 9 with an average of 10 trial participants per cluster. We further estimate an intra-class correlation coefficient (ICC) = 0.05^{101,102} and standard deviation = 16 based on similar studies.^{41,100} Given these assumptions, a sample size of $N = 180$ ($n = 90/\text{arm}$) yields 83.7% power to detect the targeted 9-point average reduction in IMAGE-HN scores between the BRIGHT and AC arms with two-sided $\alpha = 0.05$ (PASS v 08.0.13, Inequality Tests for Two Means in a Cluster-Randomized Design module).

Targeting an attrition rate = 20%, we plan to enroll 226 HNC survivors with BID to achieve our target sample size of $N = 180$ evaluable patients for the modified intention-to-treat (ITT) analyses of the efficacy population. In our pilot RCT, 20% (11/54) of eligible patients who accrued to the RCT were not evaluable for the primary endpoint: $n = 7$ (13%) went off study per protocol due to the development of recurrent HNC or a second non-HNC malignancy; and $n = 3$ (7%) withdrew due to intercurrent physical demands. No patients were lost to follow-up.

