9.3 POPULATIONS FOR ANALYSES

The **safety analysis set** (SAS) is composed of all patients enrolled who receive any part of either the BRIGHT or AC intervention. The SAS will be used to conduct all safety analyses. Patients will be analyzed based on the intervention received regardless of the assignment at randomization.

The **6-month IMAGE-HN evaluable set** is composed of all patients enrolled in the trial who have completed the baseline and 6-month follow-up IMAGE-HN survey instrument. Analysis will be performed based on assignment at randomization regardless of the intervention received (modified intent to treat). This analysis set will be used for analysis of the primary endpoint.

Analysis sets for secondary endpoints specific to PROMs at a given follow-up timepoint will be defined as the set of trial participants who have completed both the baseline and the follow-up survey at the specified timepoint. Analysis will be performed based on assignment at randomization regardless of the

intervention received (modified intent to treat). These analysis sets will be used for analysis of the secondary endpoints (**Table 5**).

The **full analysis set (FAS)** is the set of all trial participants who enroll and are eligible for the study. Patients who enroll but subsequently drop out prior to receiving any of the assigned intervention will be replaced. This analysis set will be used for secondary analyses of both the primary endpoint and secondary endpoints.

Per protocol set is composed of all patients enrolled in the trial who have completed 6-weeks of the BRIGHT/AC interventions as described in the protocol. This analysis set will be used for secondary analyses of both the primary endpoint and secondary endpoints.

Details about the analytic plan for each population are described in detail in **Section 9.4**.

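### Section 7.2 permits ending a patient's follow-up because additional, confounding treatment might be needed, which can remove patients from the primary analysis for a reason plausibly related to outcome

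*Protocol*

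**What the plan says.** Section 7.2 begins its list with "An investigator or the IRB may discontinue a participant from the study for the following reasons". The third reason on the list has two limbs. One is that further data collection would not serve the participant's best interest. The other is that an event, condition or situation "might require an additional treatment that would confound the interpretation of the study". The protocol does not say which treatments count.

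For a patient who stops only the intervention, section 7.1 is explicit: "Thereafter, the participant will be included in all future scheduled assessments, even though not participating in the intervention". Section 7.2 says nothing comparable. It asks only that the date and reason be recorded.

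Two other sections describe additional treatment as part of ordinary conduct. Under section 6.5, "participants may use antidepressants and anxiolytics at the discretion of their treating providers", with use recorded at each visit. Under section 2.3.3, the site investigator or psychologist contacts a distressed participant to "determine the need for clinical intervention beyond any treatment that they may already be receiving, and arrange appropriate mental health referral".

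Section 9.3 defines the primary set as "all patients enrolled in the trial who have completed the baseline and 6-month follow-up IMAGE-HN survey instrument". Section 9.4.2 confirms that patients without that survey are left out. Section 9.4.1 states that the primary GEE analysis is valid only if data are missing completely at random.

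**The concern.** A patient whose distress worsens is the one most likely to need more treatment and also the one most likely to have a poor 6-month IMAGE-HN score. A rule that permits follow-up to stop because more treatment might be needed can therefore create missing data related to the outcome. The trigger is broad: treatment need only be possibly required, and no treatment is named.

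The loss is also avoidable. The primary endpoint is a questionnaire, and section 7.1 shows that the trial is prepared to collect it from patients who are no longer receiving the intervention. A questionnaire that was never given cannot be recovered in a later analysis plan.

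The effect on the treatment comparison depends on whether removals differ by arm. A psychologist delivers BRIGHT and HNC clinical staff deliver AC, and section 6.3 leaves interventionists, outcome assessors and patients unblinded. A difference in how often need is noticed is possible, but the protocol gives no figure for it.

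**Working it through.** **Step 1: trace the path through the text.**

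- Section 7.2: discretionary removal from the study, with possible need for a confounding treatment as one ground.
- Sections 7.1 and 7.2 compared: assessments continue after stopping the intervention; no such statement is made after removal from the study.
- Sections 9.3 and 9.4.2: no 6-month survey means no place in the primary set.
- Section 9.4.1: the primary model needs data missing completely at random. Removal prompted by worsening after baseline does not meet that condition.
- Section 9.4.2: the secondary mixed-model and longitudinal analyses use the same evaluable set, so they do not bring removed patients back. The two full-analysis-set analyses do, by setting a missing 6-month score to the baseline score or to the maximum.

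**Step 2: reproduce the protocol's own power figure.** Inputs from section 9.2: difference 9, SD 16, ICC 0.05, 9 clusters of 10 per arm, two-sided alpha 0.05.

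- Design effect = 1 + (10 − 1) × 0.05 = 1.45
- SE = 16 × √(2 × 1.45 / 90) = 2.87
- Power from the noncentral t distribution with 18 − 2 = 16 df = 83.67%, against 83.7% stated.

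The sample size is not in error. If removals cut the evaluable number below 180, the same formula gives 82.3% at 170, 80.7% at 160 and 79.0% at 150. Lost power is a minor issue.

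**Step 3: illustrate the bias.** The protocol gives no removal shares and no outcomes for removed patients, so the following are assumptions. Let the true difference (BRIGHT minus AC) be −9. Let removed patients be D points worse at 6 months than retained patients, with the same D in both arms. Let q be the share removed in each arm.

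The mean over all patients in an arm is the retained mean plus q × D, so the retained mean is the arm mean minus q × D. Hence

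shift in the difference = D × (q in AC − q in BRIGHT).

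| D | AC removed | BRIGHT removed | Shift | Difference among completers |
|---|---|---|---|---|
| 9 | 10% | 5% | +0.45 | −8.55 |
| 9 | 15% | 5% | +0.90 | −8.10 |
| 20 | 10% | 5% | +1.00 | −8.00 |
| 20 | 15% | 5% | +2.00 | −7.00 |
| 9 | 5% | 15% | −0.90 | −9.90 |
| 20 | 5% | 15% | −2.00 | −11.00 |
| any | equal | equal | 0 | −9.00 |

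The shifts run from 0.45 to 2.0 points in size. That is 0.45/9 = 5% to 2.0/9 = 22% of the target difference, or 0.45/2.87 = 0.16 to 2.0/2.87 = 0.70 of a standard error.

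**The case against.** Much can be said for the protocol. The rule is permissive, and section 7.2 opens by saying that investigators will try to keep discontinuation low. Section 6.3 has study investigators blinded to allocation, which limits deliberate removal by arm. The distress procedure and the suicidal-ideation alert in section 2.3.3 apply to both arms, and AC staff must bring in the site psychologist if suicidality is endorsed. Section 5.5.5 accounts for the 11 of 54 pilot patients who went off study, and none is listed as removed for additional mental-health treatment. The full-analysis-set analyses would show whether the result is sensitive to such losses, and section 9.4.1 provides for a mixed model if missingness is significant. All of this stands and limits the likely size of the problem. It does not supply the missing 6-month scores.

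A reader might also infer more than the text supports:

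- *That section 7.2 flatly contradicts sections 6.5 and 2.3.3.* The clause names no treatment. It may have been meant for cancer retreatment, major surgery or outside psychotherapy, and section 6.5 suggests that permitted medication was not the target. This is a possible overlap left undefined.
- *That it contradicts section 9.3.* That section says "Analysis will be performed based on assignment at randomization regardless of the intervention received (modified intent to treat", but of a set already limited to completers. Removal changes who is in the set, not the arm in which members are analysed.
- *That deleting the clause would recover the pilot's 13% who "went off study per protocol due to the development of recurrent HNC or a second non-HNC malignancy".* Those patients could equally be removed under the best-interest limb, which the fix keeps. The losses arose under the pilot's protocol, and section 5.5.5 does not expect that rate to persist. No gain in precision can be credited to the fix on this basis.
- *That the bias could reach about 3 points in BRIGHT's favour.* This results from giving removed patients the same absolute change in both arms. With arm means of −15 and −6, removed patients at +5, and 5% (AC) and 15% (BRIGHT) removed, the retained means are (−6 − 0.25)/0.95 = −6.58 and (−15 − 0.75)/0.85 = −18.53, a difference of −11.95. That model assumes no treatment effect among those removed. Even at equal shares p it returns −9/(1 − p), which is −10.0 at 10%. Nothing in the protocol supports that assumption.

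**Conclusion.** The point holds in limited form. Section 7.2 permits follow-up to end on a ground that is plausibly related to outcome and left undefined, and the completers-only primary set then drops the patient, contrary to the missing-data condition in section 9.4.1. The reading that assessments stop rests on the contrast with section 7.1, since section 7.2 does not say what happens to them.

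Neither the frequency nor the direction of any bias can be determined from the protocol. The range of about 0.5 to 2 points rests wholly on the assumed D and removal shares, and the shift vanishes if the arms lose equal shares of equally worse patients. The change should be made because it is cheap and the data cannot be recovered later. The evidence does not support calling it a critical fault.

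**What to change.** In section 7.2, delete the possible need for additional, confounding treatment as a ground for ending data collection. State that needing or receiving additional treatment does not by itself end patient-reported follow-up. Record the treatment and its date as an intercurrent event, and analyse the collected 6-month IMAGE-HN by randomized arm. Patient request and the participant's best interest remain grounds for stopping data collection. Nothing here bears on what care a patient receives or whether the intervention continues.

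The cost is one clause in an amendment and a few more questionnaires, with no new procedures. The resulting estimate would include the effect of any additional treatment, and the report should say so.

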7.3 LOST TO FOLLOW-UP

A participant will be considered lost to follow-up if he or she fails to return for two scheduled visits and study staff are unable to contact the participant after at least 5 attempts.

The following actions must be taken if a participant fails to return to the clinic for a required study visit:

- The site will attempt to contact the participant, reschedule the missed visit within 2 weeks, counsel the participant on the importance of maintaining the assigned visit schedule and ascertain if the participant wishes to and/or should continue in the study
- Before a participant is deemed lost to follow-up, the investigator or designee will make every effort to regain contact with the participant using a variety of contact modalities (e.g., telephone call, email, text message, communication through the EHR). These contact attempts will be documented in the participant's medical record or study file.
- Should the participant continue to be unreachable, he or she will be considered to have withdrawn from the study with a primary reason of lost to follow-up.

8 STUDY ASSESSMENTS AND PROCEDURES

Each site (MUSC, HFH, WUSM) will be responsible for collecting study assessment data as described below and entering it into the REDCap eCRFs. There will be a single central REDCap developed and maintained at MUSC.

8.1 SCREENING PROCEDURES

The program coordinator at each site (MUSC, HFH, WUSM) will screen for potential participants using the EHR to preview the weekly head and neck oncology clinic schedule at each site. EHR-based screening will be supplemented by in-person collaboration with the head and neck clinical team at each site.

Research staff will review clinical documentation for all new or returning patients with an appointment in the head and neck clinic to identify patients who meet clinical study inclusion criteria and are scheduled for an appointment. Clinic rosters will be reviewed at a minimum of once per week, or more frequently if indicated by changes to the clinic schedule. As such, screening will generally be performed within 7 days of enrollment. After a patient who is potentially eligible for the study is identified, the patient will be contacted at the previously identified clinic visit within the head and neck clinic to discuss participation in the trial. All screening information and criteria necessary to establish trial eligibility

other than the IMAGE-HN score are available in the HER but will be confirmed with the patient and treating clinician

After a patient who is potentially eligible for the study is identified, the patient will be contacted at the previously identified clinic visit to discuss participation in the study as described below. The head and neck oncology clinician will notify the patient of the study and introduce the study to the potential participant. Following this introduction, if the potential participant is interested in learning additional information about the trial, the program coordinator will recruit using existing standard operating procedures for clinic-based or telemedicine-based recruitment. Patients who meet demographic and oncologic inclusion criteria will complete the IMAGE-HN as a screening assessment to identify patients with clinically significant HNC-related BID; those with score ≥ 22 will be eligible for the study.

Once a subject has signed the informed consent form (ICF), an identification number will be assigned to him/her and the study related screening procedures will start. A subject will be randomized into the study after he/she has signed the ICF and all eligibility criteria have been met.

8.2 BASELINE ASSESSMENTS

8.2.1 DEMOGRAPHIC

Demographic information is gathered as patient self-report in the eCRF. Demographic characteristics include sex, age, race, ethnicity, marital status, insurance, educational attainment, employment, and history of medication or counseling for mental health disorders.

8.2.2 CLINICAL AND ONCOLOGIC

Clinical and oncologic characteristics are assessed using clinical documentation within the EHR unless otherwise indicated.

Baseline oncologic characteristics include history of mental health diagnoses, concomitant antidepressant or anxiolytic usage, head and neck tumor subsite, tumor histology, p16/human papillomavirus (HPV) tumor status, date of treatment completion, head and neck cancer treatment modalities, type of ablative surgery, type of surgical reconstruction, American Joint Committee on Cancer (AJCC) 8th edition pathologic TNM Class, AJCC 8th edition overall pathologic stage grouping.

8.3 ENDPOINT AND OTHER NON-SAFETY ASSESSMENTS

Sites are encouraged to administer patient-reported outcome measures (PROMs) using an electronic device/tablet. If that is not feasible, administration of PROMs using a paper-based format is also acceptable. Sites are encouraged to align PROS assessments with clinic visits to facilitate in-person collection. In situations in which in-person collection is not feasible, PROMs may be collected via mail, text message, or email at the program coordinator's discretion. When possible. PROMs should be completed prior to any other study procedures (following informed consent) and before clinic visits in which clinical information will be discussed to avoid biasing the patient's responses to the questions.

8.3.1 EFFICACY

IMAGE-HN. The IMAGE-HN is a 24-item, validated, PROM of HNC-related BID.²⁷ Items are rated on a 5-point Likert scale from 'Never' (0) to 'Always' (4). The total global score is calculated by summing item responses across 21 items (all items except 3, 4, and 19). The total IMAGE-HN score on the global

domain (21 questions) ranges from 0-84; higher scores indicate worse HNC-related BID. An IMAGE-HN score of $\geq 22^4$ indicates clinically-significant HNC-related BID and a change in IMAGE-HN score of ≥ 9 points is clinically meaningful.⁸⁸

Shame and Stigma Scale in HNC. The Shame and Stigma Scale in HNC is a 20-item, validated, unidimensional PROM that measures four domains (shame with appearance, stigma, regret, and social/speech concerns) in patients with HNC over the prior 7 days.³¹ Items are rated on a 5-point Likert scale from 'Never' (0) to 'All the time' (4). The total score is calculated by summing the individual responses (except for 4 questions which are reverse scored). Shame and Stigma Scale in HNC scores range from 0-80; higher scores reflect worse HNC-related shame and stigma.

PROMIS SF v1.0- Depression 8a. The PROMIS SF v1.0-Depression 8a is an 8-item validated measure developed by the NIH to assess patient-reported negative mood, views of self, and decreased positive affect and engagement.⁸⁹ Responses rate the strength of agreement with statements about depressive symptoms using a scale that ranges from 1-5. The total raw score is calculated by summing the individual responses. The PROMIS SF v1.0-Depression 8a raw score ranges from 8-40; a higher score reflects more severe depressive symptoms. The PROMIS SF v1.0-Depression 8a total raw score is translated into a T-score for each participant according to the PROMIS Scoring manual. The T-score provides a standardized score with a mean of 50 and a standard deviation of 10.

PROMIS SF v1.0-Anxiety 8a. The PROMIS SF v1.0-Anxiety 8a is an 8-item, validated, developed by the NIH to assess patient-reported fear, worry, and hyperarousal.⁸⁹ Responses rate the strength of agreement with statements about anxiety symptoms using a scale that ranges from 1-5. The total raw score is calculated by summing the individual responses. The PROMIS SF v1.0-Anxiety 8a raw score ranges from 8-40; a higher score reflects more severe anxiety symptoms. The PROMIS SF v1.0-Anxiety 8a total raw score is translated into a T-score for each participant according to the PROMIS Scoring manual. The T-score provides a standardized score with a mean of 50 and a standard deviation of 10.

Beck Scale for Suicidal Ideation. The Beck Scale for Suicidal Ideation is a 21-item, validated, patient-self report rating scale to rate the severity of a patient's suicidal thoughts and plans.⁹⁰ Each item consists of three options graded according to suicidal intensity from 0 to 2. The ratings for the first 19 items are summed to yield a total score, which ranges from 0 to 38. Higher scores represent more severe suicidal ideation.⁹¹ A cutoff score of > 2 is optimal to indicate high/low risk of suicidal ideation.⁹²

PROMIS SF v2.0-Ability to Participate in Social Activities 8a. PROMIS SF v2.0-Ability to Participate in Social Activities 8a is an 8-item, validated, unidimensional measure of patient-reported perceptions of participation in social activities.^{93,94} Items are scored using a 5-point Likert scale from 'Never' (1) to 'Always' (5). The total raw score is calculated by summing the individual responses. The total raw score ranges from 8-40; a higher score reflects more severe inability to participate in social activities. The total raw score is translated into a T-score for each participant according to the PROMIS Scoring manual. The T-score provides a standardized score with a mean of 50 and a standard deviation of 10.

EORTC QLQ-HN35 Trouble with Social Eating Subscale. The EORTC QLQ-HN35 Trouble with Social Eating Subscale is a 4-item, validated measure of trouble with social eating for patients with HNC.⁹⁵ The subscale is composed of QLQ-H&N35 items 19-22. Items are scored using a 4-point Likert scale from 'not at all' (0) to 'very much' (3). The total score is calculated by summing the individual responses. Total subscale scores range from 0-12; higher scores reflect more trouble with social eating.

EORTC QLQ-HN35 Trouble with Social Contact Subscale. The EORTC QLQ-HN35 Trouble with Social Contact Subscale is a 5-item, validated measure of trouble with social contact for patients with HNC.⁹⁵ The subscale is composed of QLQ-H&N35 items 18, 25-28. Items are scored using a 4-point Likert scale from 'not at all' (0) to 'very much' (3). The total score is calculated by summing the individual responses. Total subscale scores range from 0-15; higher scores reflect more trouble with social contact.

